#### Administration of Questionnaires/Surveys Timeline/Treatment

All visits will be scheduled as a part of the research study and design. The 1-week survey will be completed prior to the third treatment. The investigators will contact the participant to electronically send the 1-month, 3-month and 6-month follow-up questionnaires. Each GROC is administered prior to the next treatment. The Pain Diagram, NDI, NPRS, FABQ are administered at the time points.

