- 11. Inability to legally provide informed consent for any other reason.
- 12. Inability to comply with the treatment and follow-up schedule.

Due to the unknown effect of cervical TJM in pregnancy due to a lack of rigorous scientific research, women who are known to be pregnant or lactating will not be included in this study. If an individual becomes pregnant during the first month of the study, investigators will discontinue their manual therapy treatment but continue follow-up assessments in accordance with the intention-to-treat protocol.

Once patients are admitted to the study, no patient will be removed for non-compliance. Use of medication will not be controlled. However, to minimize its effect, patients will be instructed to continue taking their current medications as prescribed and not to start any new medications during the one-week and 4-week follow-up period. Current medication usage will be recorded at baseline. Additionally, at the 3 and 6-month follow-up investigators will collect data on medication usage as well as additional physical therapy visits and other healthcare interventions the patient may have received.

This study will include both genders and members of minority groups. The investigators will attempt to recruit patients in respective proportion to the demographics of each of the data collection clinic's respective geographic locations. No individuals will be excluded from participation in this study on the basis of race, creed, color, gender, national or ethnic origin, sexual orientation, disability, or health status.

Patients attending for physical therapy at any one of the 4 clinical sites will be screened for eligibility to participate in the study (neck pain duration of <38 days, once treatment blocks are filled for those subjects negative on the CPR). Physical Therapists trained in the study protocol will further evaluate participants by completing a medical screening process and a detailed history and physical examination for inclusion and exclusion criteria and obtain informed consent. Informed consent will be obtained within a private office setting. Subjects will have an opportunity to fully review the informed consent, ask questions, and determine independently if they want to participate in the research study.

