# Identification of the Status on the Rule

As in the initial study, patients meeting at least three of the following criteria will be classified as meeting the CPR (+) for cervical TJM. Patients meeting two or fewer criteria will be classified as not meeting the CPR (-):

1. Symptom duration less than 38 days

- 2. Positive expectation that TJM will help
- 3. Side-to-side difference in cervical rotation range of motion of 10° or greater
- 4. Pain with posteroanterior spring testing of the middle cervical spine

Based on previous results, these criteria increase the likelihood of a *successful* response with cervical TJM from an initial 39% to 90%. Patients who rated their perceived recovery on the GROC as "a very great deal better", "a great deal better", or "quite a bit better" (i.e., a score of +5 or greater) were judged as a success. This degree of improvement over a 2–4-day period was deemed to provide an adequate distinction between patients responding to the intervention and those simply benefiting from the favorable natural history of neck pain. For those *not* meeting *at least 3* of the 4 criteria, the likelihood of a successful response only rose from 39% to 43% (1 criterion) or 68% (2 criteria). Once the examination is complete patients will be randomly assigned to one of the two groups regardless of their status on the CPR: 1) MTE or 2) MoE.

A random number generator will be used to conduct the randomization, and this procedure will be conducted prior to the initiation of the study. The randomization will be concealed according to the following procedure:

- The group assignment will be recorded on a label that is affixed to a 3.5 X 5-inch index card which will be folded in half. The folded index card will then be placed inside the envelope, and the envelope will be sealed.
- Once the baseline examination is complete, the randomization envelope will be handed to a treating therapist who is blinded to the initial baseline examination; she/he will open the envelope, and the treatment will begin according to group assignment under the supervision of the treating therapist.

Treatment will be initiated immediately following the baseline examination, unless prohibited by time constraints; in this case the patient will be scheduled for a follow-up session within 24 to 48 hours of the initial examination to receive the first treatment.

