# Treatment Sessions #3, 4, and 5:

The treatment program consists of three components: 1) warm-up exercises for 10 minutes, 2) a program of stretching and strengthening exercises for the cervical, thoracic and shoulder complex, and 3) advice to return to usual physical, work and recreational activity.

The third and subsequent treatment sessions will occur within 5-7 days of each previous treatment session. At each of these treatment sessions, patients will complete a GROC based on their

perceived recovery since the baseline examination. As well as the GROC, all patients will complete a follow up NPRS, FABQ and NDI at the beginning of visits #3 (1 week) and #5 (1 month).

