# 7.0 STATISTICAL ANALYSIS

This study will collect quantitative data. Data will be collected from 140 participants. Data includes survey data self-reported and collected from participants at baseline, one week, one month, three months, and six months, as well as self-reported demographic information. To ensure confidentiality, all data that is electronically transmitted will only be identifiable by the subject's case number, which will be recorded on the forms. No confidential information such as the subject's name, address, phone number, or any other information that might possibly be used to link the data back to the subject will be transmitted. This will ensure that confidentiality is maintained. All subject information will be handled in a confidential manner consistent with other medical records. Full compliance with HIPAA standards will be upheld throughout the investigation to protect participant privacy and confidentiality. All electronic data will be secured in password protected cloud storage. This research study will minimize the use of paper records. All hardcopy records pertaining to a subject's involvement in this research study will be stored in a locked file cabinet at each of the sites in which the study is to be conducted. A case number will indicate the subject's identity on these records. This information will only be accessible to the investigators, their research study staff, and

the physical therapists involved in providing the treatment. Participants will not be specifically identified in any publication of research results. Research records will be kept for a period of not less than five years from the completion of the study.

The programs utilized to store data will be password protected, including Box, Microsoft Teams, Baylor Microsoft OneDrive. The investigators will not have access to any of the data until final de-identification is complete. All data will be collected using Qualtrics surveys incorporating all questionnaires hosted on a tablet device at each respective clinic site collecting data. The 3-month and 6-month data collection link will be sent electronically to each participant.

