Specific Aims: Primary Aim #1: To determine the validity of the clinical prediction rule for identifying patients with neck pain who are likely to benefit from C-TJM. Pain and Disability. The investigators will examine the primary aim with separate random intercept linear mixed models with treatment group (MTE vs. MoE), status on the CPR (positive or negative) and time (baseline, 1-week and 4weeks) as fixed effects. The dependent variables will be pain (NPRS) and disability (NDI score). The hypothesis of interest is the group \* CPR status \* time interaction. The primary dependent variables are the 1-week NPRS and NDI scores to mirror the follow-up used in Cleland and colleagues' study. The investigators will assess the NPRS and NDI scores after 4 weeks to determine whether a patient's status on the rule predicts outcome at a longer follow-up. The investigators will perform planned pairwise comparisons at each follow-up period by using the Bonferroni test of inequality. The investigators hypothesize that patients who are positive on the rule and receive TJM will achieve greater improvement in immediate (1-week) and 4-week pain and disability, than patients who are negative on the rule and receive TJM, and compared to patients who are positive on the rule but receive an alternative exercise program without TJM. Because the rule is believed to be specific to a TJM intervention, investigators hypothesize that outcomes among those receiving the MoE treatment would not differ on the basis of a patient's status on the rule.

Secondary Aim #1: To compare the long-term (6-month) pain and disability scores (clinical

outcomes) and healthcare utilization based on status on the clinical prediction rule and the treatment received. The investigators will examine this with random intercept linear mixed models with treatment group (MTE vs. MoE), status on the CPR (positive or negative), and time (baseline and 6-months) as fixed effects. The dependent variables will be pain (NPRS) and disability (NDI) scores. The investigators will perform planned pairwise comparisons at each follow-up period by using the Bonferroni test of inequality. The hypothesis of interest is the group \* status on CPR \* time interaction. The investigators hypothesize that patients who are positive on the rule and received TJM would experience greater improvement at 6-months than patients who are negative on the rule and received the MoE program without TJM.

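### The plan states no way to collect the primary 1-week NDI and NPRS from a patient who misses treatment session 3

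*Combined protocol and SAP*

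**What the plan says.** **The outcome.** Section 7.0, Data Analysis, states: "The primary dependent variables are the 1-week NPRS and NDI scores". The Sample Size and Power paragraph sizes the trial on the 1-week NDI.

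**How it is collected.** Section 5.0, Administration of Questionnaires/Surveys Timeline/Treatment, says: "The 1-week survey will be completed prior to the third treatment". The text on sessions 3 to 5 for both arms places the NDI, NPRS and FABQ at the start of visit 3. The schedule table and Appendix G label the 1-week time point as visit 3. Section 7.0 describes the questionnaires as "hosted on a tablet device at each respective clinic site collecting data". Electronic sending is described for 1, 3 and 6 months in Section 5.0 and for 3 and 6 months in Section 7.0. One week is in neither list.

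**Who stays in.** Section 3.0 says: "Once patients are admitted to the study, no patient will be removed for non-compliance". Section 4.0, item 4, analyses every participant as assigned, whatever treatment was completed.

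**Missing values.** The end of the intervention text in Section 5.0 carries the last appointment's results forward for participants who terminate early. The Missing Data paragraph of Section 7.0 relies on a mixed model under missing at random, with imputation and sensitivity analyses if much is missing.

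**The concern.** The primary time point is the one follow-up with no stated route outside a treatment visit. A patient who stops attending after session 1 or 2 remains in the trial and is sent the later surveys, but the plan describes no way to obtain that patient's primary outcome.

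Whether the value exists then depends on attendance. Attendance may plausibly depend on early recovery, on soreness (Section 6.0 gives 1% to 25% after manipulation) or on disappointment with the allocation. Expectation of benefit from manipulation is itself an item of the prediction rule, so disappointment could differ across the four treatment-by-rule cells. Missingness of that kind would strain the missing-at-random assumption, and a 1-week score not obtained at the time cannot be recovered later.

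**Working it through.** **1. The plan's own sample size.** Inputs from Sample Size and Power: difference 10 points, SD 12, two-sided alpha 0.05, power 90%.

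n per cell = 2 × (1.960 + 1.282)² × 12² / 10² = 30.3, rounded up to 31. This reproduces the stated figure.

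**2. The allowance.** 140 / 4 = 35 recruited per cell. 35 − 31 = 4 missing values tolerated per cell; 4 / 35 = 11.4%. Power by number observed (normal approximation, difference 10, SD 12):

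| Observed per cell | Missing | Power |
|---|---|---|
| 35 | 0% | 93.7% |
| 31 | 11.4% | 90.7% |
| 28 | 20% | 87.7% |
| 25 | 28.6% | 83.8% |

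**3. When visit 3 falls.** Session 2 follows session 1 by 2 to 4 days. For session 3: "The third and subsequent treatment sessions will occur within 5-7 days of each previous treatment session". So visit 3 is at day 2 + 5 = 7 to day 4 + 7 = 11 after first treatment. If treatment cannot start at once, the patient is "scheduled for a follow-up session within 24 to 48 hours of the initial examination to receive the first treatment"; adding 2 days gives at most day 13 after the baseline scores.

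**4. What is known about a patient who misses session 3.** The schedule table and Appendix G show only the GROC at visit 2. Before the gap there is therefore one NDI and one NPRS value, at baseline. Two cases follow:
- Early termination: the carried-forward score is the baseline score, so the 1-week change is zero.
- No termination: the 1-week value is missing. The primary mixed model uses the baseline value and, if returned, the 4-week value. The GROC is not in that model.

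**5. Illustration of the carry-forward case.** Assumptions not in the documents: the share d missing session 3; all of them terminate early; comparator mean improvement m of 0 or 5 points. The true difference is 10, the SD 12, with 35 per cell.

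Observed difference = (10 + m)(1 − d₁) − m(1 − d₂), where d₁ is the manipulation cell and d₂ the comparator. Variance in a cell with mean change A = (1 − d) × 144 + d(1 − d) × A².

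Example with d₁ = 20%, d₂ = 5%, m = 0: difference 10 × 0.8 = 8.0; variances 131.2 and 136.8; SE = √(268.0 / 35) = 2.77; power = Φ(8.0 / 2.77 − 1.96) = 82%.

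| d₁ / d₂ | Difference (m = 0; m = 5) | Power (m = 0; m = 5) |
|---|---|---|
| 10% / 10% | 9.0; 9.0 | 90%; 89% |
| 20% / 20% | 8.0; 8.0 | 85%; 82% |
| 20% / 5% | 8.0; 7.25 | 82%; 71% |
| 5% / 20% | 9.5; 10.25 | 94%; 96% |

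The distortion can go in either direction, depending on which cell loses more patients.

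**The case against.** Collecting an outcome at a visit is an ordinary choice, and the plan has safeguards. It excludes people unable to keep the treatment and follow-up schedule, pays incrementally for completed follow-up, reports drop-outs with reasons, and has missing-data methods. The 4-week scores enter the primary model and inform a missing 1-week score. Section 3.0 also shows that assessment can be separated from treatment: a participant who becomes pregnant in the first month stops manual therapy but continues follow-up. All of this stands, and it limits the harm.

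Four stronger readings go beyond the documents:
- A reader might infer that remote 1-week collection is ruled out. No passage forbids it, and the lists of electronic surveys do not agree with each other about 1 month. What is supported is that no other route is stated.
- A reader might infer that visit 3 can fall at any time. It has an implied window of day 7 to 11, the same in both arms, and Section 9.0 has deviations reported to the IRB. Spread among patients who keep the schedule adds noise and is not shown to bias the contrast. What is missing is a rule for the survey when the session falls outside that window.
- A reader might put a figure on the bias: 4 / 35 × 10 = 1.1 points in one cell, or 2.3 with opposite selection in two. This borrows the treatment target as the gap between attenders and non-attenders, and assigns the whole allowance to missed sessions. The documents support neither step.
- A reader might want every patient surveyed at day 7 after baseline. That falls 3 to 5 days after session 2 (7 − 4 to 7 − 2), or 1 to 3 days if first treatment is 48 hours late, instead of the present 5 to 7. Section 6.0 says symptoms after treatment typically resolve within 1 to 48 hours, so some answers could fall in that period. It exchanges one timing spread for another.

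**Conclusion.** The gap is real and lies in data collection. As written, a patient who misses session 3 has no 1-week NDI or NPRS, or has the baseline score carried forward after early termination, and a postponed session gives a late value. This does not remove anyone from the analysis set, and the intention-to-treat statement stands. It does make the presence of the primary outcome depend on attendance.

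The size cannot be derived from the documents, because no rate of missed sessions is given. The fixed points are the 11.4% allowance and 90.7% power at 31 per cell. The 71% to 96% range in the carry-forward illustration rests wholly on assumed rates, on assumed comparator improvement and on treating all missed sessions as early termination. The change is worth making because it is cheap and protects the outcome on which the trial is sized.

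**What to change.** Keep the 1-week assessment before session 3 for patients who attend within day 7 to 11 after first treatment. In Section 5.0 (sessions 3 to 5 for both arms, the schedule table and the questionnaire administration paragraph) and in Appendix G, add:
- Any randomised patient who has not completed session 3 by the end of that window is sent the existing Qualtrics 1-week survey (NDI, NPRS, FABQ, GROC) electronically, whether or not treatment continues.
- The completion date is recorded for everyone.

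The text should also say which value counts if a patient answers the link and later attends session 3, and from which date the window runs for a randomised patient who never starts treatment. Treatment timing does not change, and patients are not all re-anchored to day 7 after baseline.

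The cost is a short protocol edit and one more survey link. Some 1-week answers will be given at home instead of in clinic, and this will be linked to non-attendance. Some non-attenders may still not respond, so the missing-data methods remain necessary.

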# 6.0 RISKS & BENEFITS

Participation in this study carries minimal risk. The examination and procedures used are common practices among physical therapists treating neck pain. There are a few small risks for consideration. After treatment, participants may experience: 1) general soreness (uncommon), 2) dizziness (rare), or 3) nausea (rare). These symptoms typically resolve within 1-48 hours.

The chance of increased pain intensity from exercise is rare, occurring in less than 1% of individuals (less than 1 out of 100). The chance of mild muscle soreness after TJM is slightly more common, occurring in 1%-25% of individuals (1-25 out of 100).

The investigators will attempt to minimize soreness following exercise by ensuring a licensed physical therapist instructs all participants in proper exercise technique. In addition, a physical therapist will re-examine a participant, at any time, if appropriate. The investigators have minimized the risks associated with TJM by ensuring that the licensed physical therapists participating in this study already routinely use TJM in the management of their patients with neck pain. The investigators have further minimized these risks by ensuring that each physical therapist participating in the study will have been specifically trained in the use of the TJM techniques used in this study. Additionally, all potential research participants will be screened to ensure they do not exhibit any exclusion criteria which may place them at increased risk for complication.

If it's discovered during the examination that the participant is excluded from the study and may have symptoms consistent with a central nervous system disorder or cervical vascular disorder, the examining physical therapist will inform the participant of the noted exclusionary criteria and recommend the individual see their primary care provider for further screening and evaluation.

While additional medical or psychological resources are not anticipated to be necessary given the study's focus on standard treatments, participants who request such resources will have access to them through their healthcare system's standard procedures.

The primary benefit participants may experience from this study is an improvement in their neck pain. All participants will be compensated financially for their time and participation in the study. Additionally, participants may find value in contributing to the advancement of medical science by helping to identify the most effective treatments for neck pain.

# 7.0 STATISTICAL ANALYSIS

This study will collect quantitative data. Data will be collected from 140 participants. Data includes survey data self-reported and collected from participants at baseline, one week, one month, three months, and six months, as well as self-reported demographic information. To ensure confidentiality, all data that is electronically transmitted will only be identifiable by the subject's case number, which will be recorded on the forms. No confidential information such as the subject's name, address, phone number, or any other information that might possibly be used to link the data back to the subject will be transmitted. This will ensure that confidentiality is maintained. All subject information will be handled in a confidential manner consistent with other medical records. Full compliance with HIPAA standards will be upheld throughout the investigation to protect participant privacy and confidentiality. All electronic data will be secured in password protected cloud storage. This research study will minimize the use of paper records. All hardcopy records pertaining to a subject's involvement in this research study will be stored in a locked file cabinet at each of the sites in which the study is to be conducted. A case number will indicate the subject's identity on these records. This information will only be accessible to the investigators, their research study staff, and

the physical therapists involved in providing the treatment. Participants will not be specifically identified in any publication of research results. Research records will be kept for a period of not less than five years from the completion of the study.

The programs utilized to store data will be password protected, including Box, Microsoft Teams, Baylor Microsoft OneDrive. The investigators will not have access to any of the data until final de-identification is complete. All data will be collected using Qualtrics surveys incorporating all questionnaires hosted on a tablet device at each respective clinic site collecting data. The 3-month and 6-month data collection link will be sent electronically to each participant.

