#### 2. Blinding

- Outcome assessors are blinded to both the treatment group and the participant's CPR status. This minimizes the risk of measurement bias, as the assessors' expectations cannot influence the evaluation of outcomes.
- The therapists administering the treatment are blinded to the participants' CPR status and the outcomes of follow-up assessments. This prevents the therapists from altering their approach based on knowledge of the participant's predicted likelihood of improvement, thereby maintaining treatment consistency across groups.
- The therapist performing the baseline examination is blinded to the participants' treatment group and the outcomes of follow-up assessments. This prevents the baseline examiner from altering their approach based on the knowledge of the participant's treatment or likelihood of improvement, thereby maintaining treatment consistency across groups.

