# Sharing study results:

The only screening procedure involved in the study is a physical exam by a licensed physical therapist. If the exam results in an unanticipated finding, the physical therapist will share that information with the participant and refer the participant back to his/her primary care provider for follow-up.

Participants will be given a verbal summary of their general examination results at the end of their first study session. However, the clinical utility of the details of the examination findings will not be fully understood until analysis has been completed. The investigators, therefore, do not plan to formally share the examination findings with either the participant or their primary care provider.

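### Section 7.0 gives treating therapists access to subject records with no exclusion for rule or outcome data, which contradicts the therapist blinding in 4.0 and 5.0 and the access limit in 8.0

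*Combined protocol and SAP*

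**What the plan says.** Blinding. Section 4.0, item 2: "The therapists administering the treatment are blinded to the participants' CPR status and the outcomes of follow-up assessments". The stated purpose is to stop therapists changing their approach according to a patient's predicted response. Section 5.0, Identification of the Status on the Rule, adds that after the baseline examination "the randomization envelope will be handed to a treating therapist who is blinded to the initial baseline examination". That sentence covers the baseline examination only.

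Access to records. Section 7.0: "All hardcopy records pertaining to a subject's involvement in this research study will be stored in a locked file cabinet at each of the sites" where the study runs, labelled by case number. Then: "This information will only be accessible to the investigators, their research study staff, and" (the sentence continues after a page break, and the next one turns to publication) "the physical therapists involved in providing the treatment. Participants will not be specifically identified in any publication of research results". Section 8.0, under Non-identifying data, has a different rule for Baylor and each clinic during data collection: only the principal investigator and one co-investigator with no part in data collection or treatment.

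Contents of the records. The opening of 8.0 says the research material may be electronic or hard copy and includes cervical range of motion and special-test findings. Section 7.0 says that paper will be kept to a minimum and that data are collected in Qualtrics. Section 8.0, on data capture, still provides for hard-copy questionnaires.

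Disclosure to patients. Section 8.0, Sharing study results: "Participants will be given a verbal summary of their general examination results at the end of their first study session". It does not say who gives the summary or whether rule items are left out. The same paragraph says that findings will not be formally shared.

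**The concern.** All four rule items are baseline data. Rotation asymmetry and spring-test pain come from the physical examination; onset date and expectation of manipulation come from the baseline forms. Anyone holding a complete baseline file can count the items and classify the patient.

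The blind matters for this hypothesis in particular. The trial asks whether manipulation (the MTE arm, against mobilization in MoE) works better in rule-positive patients. The therapists already use manipulation routinely (6.0), and in the MTE arm they choose the level and may make up to two attempts per side (5.0, MTE Group). The outcomes are self-reported, so blinding the assessors does not remove an influence that acts through the therapist or the patient. If a therapist who knew rule status favoured rule-positive MTE patients, the effect would fall in that one cell. It would enter both planned comparisons and the group by CPR interaction in full, in the direction that validates the rule.

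**Working it through.** **1. The access and blinding rules side by side.**

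| Place | Treating therapist's position | Exception or time limit |
|---|---|---|
| 4.0, item 2 | Must not know CPR status or follow-up outcomes | None |
| 5.0, Status on the Rule | Must not know the baseline examination | Silent on follow-up outcomes |
| 7.0, data handling | On the list of those with access to subject records | None |
| 8.0, Non-identifying data | Excluded; two named roles only | During data collection |

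The third row conflicts with the other three, and nothing says which prevails.

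**2. Could the records reveal rule status?** Status is positive with at least three of four items. Duration and expectation are on the demographic and treatment-expectations forms; rotation and spring testing are in the physical examination. The opening of 8.0 includes range of motion and examination findings in the research material, in either format. A complete file is therefore enough. How much of it will be on paper at a site is not stated.

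**3. Timing.** Treatment normally starts straight after the baseline examination, and manipulation or mobilization is given at visits 1 and 2. The 1-week survey comes before treatment 3. The verbal summary at the end of the first session therefore normally falls after treatment 1 and before treatment 2. When first treatment is deferred by 24 to 48 hours, and if the first study session then means the examination alone, the summary precedes both. The only follow-up measure before the 1-week outcome is the global rating of change at visit 2.

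**4. The plan's own figure.** Inputs from 7.0, Sample Size and Power: difference 10, SD 12, two-sided alpha 0.05, power 90%.

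n per cell = 2 × (1.960 + 1.282)² × 12² / 10² = 30.3, rounded up to 31. This matches the plan and does not depend on the present point.

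**5. Illustration of size.** The documents give no bias, so the shift b in the CPR-positive MTE cell is assumed. With 35 per cell and no true difference, two-sided error = 1 − Φ(1.96 − b/SE) + Φ(−1.96 − b/SE).

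- One pairwise contrast: SE = 12 × √(2/35) = 2.87
- Interaction (difference of two differences): SE = 12 × √(4/35) = 4.06

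| Assumed b (NDI points) | Share of 10-point design difference | Error, pairwise | Error, interaction |
|---|---|---|---|
| 0 | 0% | 0.050 | 0.050 |
| 1 | 10% | 0.064 | 0.057 |
| 2 | 20% | 0.107 | 0.078 |
| 3 | 30% | 0.182 | 0.115 |
| 5 | 50% | 0.414 | 0.234 |

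These are for single tests at 0.05 on change scores, before the planned Bonferroni adjustment.

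**The case against.** The strongest reply is that the 7.0 sentence is confidentiality wording. It sets an outer limit on who may see records; it does not say that therapists will consult them while treating. Its nearest antecedent is the hard-copy file, in a study that keeps paper to a minimum and enters data in Qualtrics. The 8.0 rule is more specific, covers the clinics and excludes anyone involved in treatment. Bias would also require a therapist to open the file, work out rule status and then treat differently within a standardized manual.

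Much of this stands. A reader might infer that the blind is undone before the 1-week outcome. The documents do not support that, because permission to see a record is not evidence that it is read. Nor do they support the idea that follow-up NDI or pain scores could leak before the 1-week endpoint, since only the visit 2 global rating exists by then. The blind to follow-up outcomes rests on 4.0 alone.

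The verbal summary is also easy to overstate. It is general, it goes to the patient, and CPR status is not mentioned. Patients already know their duration, their expectation and whether spring testing hurt, so it could add rotation asymmetry at most. If the baseline examiner gives it after treatment, the examination is already finished and cannot be biased by that contact.

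The contradiction itself remains. Minimal paper is not no paper, and 8.0 provides for hard-copy data. A site following 7.0 as written could open the whole file to the treating therapist and still be within the protocol.

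**Conclusion.** The point holds as a contradiction in the text that leaves a key blind unprotected. Section 7.0 permits access that 4.0, 5.0 and 8.0 rule out, and the material concerned is enough to derive rule status. The summary at the first session is a secondary gap: the speaker is not named and rule items are not excluded.

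It does not show that any therapist is or will be unblinded. The size of any bias is unknown. The error rates above rest wholly on an assumed shift, with the plan's SD of 12 and 35 per cell, and show only the direction and scale that such a shift would have. The sample size is unaffected.

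The correction is still worth making: 4.0 relies on this blind, any bias would favour the trial's own hypothesis, and a blind cannot be restored once patients have been treated.

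**What to change.** In 7.0, remove treating therapists from access to baseline-examination, expectation, CPR and outcome records, electronic or paper, at least until the patient's treatment sessions and 4-week outcomes are complete. Give them a sheet with participant ID, allocated arm and safety information only. Cross-refer to 4.0, 5.0 and 8.0 so that one rule governs.

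In 8.0, Sharing study results, state that the baseline examiner gives the summary before the envelope is opened, that it omits rotation asymmetry, spring-test findings and rule status, and that patients are asked not to discuss it with the treating therapist. Unanticipated findings continue to be shared and referred at once, as 8.0 already provides.

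The cost is a few sentences of protocol text, a file-access setting at each site, and slightly less detail for patients at visit 1. Patients could still mention their duration or expectation unprompted, and this change does not prevent that.
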